9.1 Sample Size Calculation

This study uses a single-arm design to test for an improvement in response rate in the HL population. A sample size of 100 will provide a robust population for safety evaluation and adequate precision for observed ORR in the expected range. For the test of efficacy, this study has > 98% power to distinguish between an active therapy with a 55% true response rate from a therapy with a response rate of 35% or less with a 1-sided alpha of 0.025.

9.2 Analysis Populations

- All-Treated Population: All patients who receive at least 1 dose of camidanlumab tesirine. This population will be used in the primary analyses of efficacy and safety.
- Per-Protocol Population: All patients in the all-treated population without important protocol deviations, which will be further described in detail in the SAP.
- The PK Population: All patients who receive study drug and have at least 1 pre- (C1D1) and 1 postdose valid assessment.
- The Pharmacodynamic Population: All patients who receive study drug and have at least 1 valid pharmacodynamics/biomarker assessment.

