5.2 Exclusion Criteria

- 1. Previous treatment with camidanlumab tesirine.
- 2. Participation in another investigational interventional study. Being in follow-up of another investigational study is allowed.
- 3. Known history of hypersensitivity to or positive serum human anti-drug antibody (ADA) to a CD25 antibody.
- 4. Allogenic or autologous HSCT within 60 days prior to start of study drug.
- 5. Active graft-versus-host disease (GVHD), except for non-neurologic symptoms as a manifestation of mild (≤ Grade 1) chronic GVHD.
- 6. Post-HSCT lymphoproliferative disorders.

- 7. Active second primary malignancy other than non-melanoma skin cancers, non-metastatic prostate cancer, in situ cervical cancer, ductal or lobular carcinoma in situ of the breast, or other malignancy that the Sponsor's medical monitor and Investigator agree and document should not be exclusionary.
- 8. History of symptomatic autoimmune disease (e.g., rheumatoid arthritis, systemic progressive sclerosis [scleroderma], systemic lupus erythematosus, Sjögren's syndrome, autoimmune vasculitis [e.g., Wegener's granulomatosis]) (subjects with vitiligo, type 1 diabetes mellitus, residual hypothyroidism, hypophysitis due to autoimmune condition only requiring hormone replacement may be enrolled).
- 9. History of neuropathy considered of autoimmune origin (e.g., polyradiculopathy including Guillain-Barré syndrome and myasthenia gravis) or other central nervous system autoimmune disease (e.g., poliomyelitis, multiple sclerosis).
- 10. History of recent infection (within 4 weeks of C1D1) considered to be caused by one of the following pathogens: HSV1, HSV2, VZV, EBV, CMV, measles, Influenza A, Zika virus, Chikungunya virus, mycoplasma pneumonia, *Campylobacter jejuni*, enterovirus D68, or severe acute respiratory syndrome coronavirus 2 (SARS-CoV-2).
 - Note: An influenza test and a pathogen-directed SARS-CoV-2 test (such as polymerase chain reaction [PCR]) are mandatory and must be negative before initiating study treatment (tests to be performed 3 days or less prior to dosing on C1D1; an additional 2 days are allowed in the event of logistical issues for receiving the results on time).
- 11. Patients who are carriers of human immunodeficiency (HIV) virus, hepatitis B virus (HBV), or hepatitis C virus (HCV), and require anti-viral therapy or prophylaxis.

 Note: Serology testing is mandatory for patients with unknown status.

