7.5.1 Pharmacokinetics

The PK profile of camidanlumab tesirine PBD-conjugated antibody, total antibody, and unconjugated warhead SG3199 will be assessed in serum by a central laboratory designated by the Sponsor using validated bioanalytical methods.

Up to 6 mL of whole blood will be collected as per Table 1 and Table 4. Blood should be drawn from a vein away from the one used for study drug infusion.

The serum PK samples must be stored at \leq -70°C. Please refer to the laboratory manual for detailed instructions regarding specimen handling and shipment.

At timepoints coinciding with ECG collection, PK blood collection should occur immediately after the end of the ECG recording and, when applicable, after vital signs (example in Figure 2). If a patient experiences Torsade de Pointes, concomitant PK samples (e.g., unscheduled) should be collected.

Table 4 Sampling Schedule for PK and ADA

Cycle	Day	PK timepoint (window)	ADA timepoint (window)
C1	D1	Predose (preferably within 2 h prior to start of infusion)	Predose (preferably within 2 h prior to start of infusion)
		EOI (-5 to +10 min) Postdose* 4 h (± 10 min)	
	D8	Postdose* 168 h (± 48 h)	-
	D15	Postdose* 336 h (± 48 h)	Postdose* 336 h (± 48 h)
C2	D1	Predose (within 2 h prior to start of infusion)	Predose (within 2 h prior to start of infusion)
		EOI (-5 to +10 min)	
		Postdose* 4 h (± 10 min)	
	D8	Postdose* 168 h (± 48 h)	-
	D15	Postdose* 336 h (± 48 h)	-
C3, C4, C5, and C6	D1	Predose (within 2 h prior to start of infusion)	-
		EOI (-5 to +10 min)	
C3, C5,	D1	-	Predose (within 2 h prior to start of
every other cycle			infusion)
C7, C8,	D1	Predose (within 2 h prior to start of	-
every cycle		infusion)	

Cycle	Day	PK timepoint (window)	ADA timepoint (window)
ЕОТ		At any time during visit day	At any time during visit day
Unscheduled			Any time (if applicable, together with PK sample)

Abbreviations: ADA, anti-drug antibody; EOI, end of infusion; EOT, end of treatment; PK, pharmacokinetics.

To understand the metabolic disposition of camidanlumab tesirine in humans, samples remaining after PK analysis is complete may be pooled among patients for potential metabolite identification.

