9.9 Pharmacokinetic Analyses

The PK profile will include determination of maximum concentration (C_{max}), time to C_{max} (T_{max}), area under the concentration-time curve from time zero to the last quantifiable concentration (AUC_{last}), area under the concentration-time curve from time zero to the end of the dosing interval (AUC_{tau}), area under the concentration-time curve from time zero to infinity (AUC_{inf}), apparent terminal elimination half-life (T_{half}), clearance (CL), volume of distribution (V_{ss}), and accumulation index (AI).

PK parameters will be determined for all PK-evaluable patients using a non-compartmental population PK analysis using Phoenix WinNonlin (Certara US, Inc., Princeton, NJ, US) or other appropriate software. Supplemental integrated population PK analyses will be undertaken and reported separately to evaluate the population PK parameters for the typical patient and to identify covariate factors which influence drug disposition.

Potential correlations of PK parameters to Baseline characteristics and safety observations will be assessed but may be reported separately. In addition, the influence of camidanlumab tesirine PBD-conjugated antibody and unconjugated warhead SG3199 concentrations on the QTc interval will be assessed but reported separately.

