3.3 Modifications to the statistical section of the protocol

NA.

4 Statistical methods

All analyses use SAS® version 9.4 or higher. All available data will be used in the analyses, and important data will be included in data listings, sorted by patient, and by visit within patient. Missing data will not be imputed, except via censoring in survival analyses and as otherwise specified.

Unless otherwise noted, categorical data will be presented using counts and percentages, with the number of patients in the analysis population as the denominator for percentages. Percentages will be rounded to one decimal place, except 100% will be displayed without any decimal places and percentages will not be displayed for zero counts. Continuous data, unless otherwise noted, will be summarized using the number of observations (n), mean, standard deviation (std), median, minimum, and maximum. Minima and maxima will be rounded to the precision of the original value, and means, medians, and 95% confidence intervals (CIs) if presented will be rounded to 1 decimal place greater than the precision of the original value. The std will be rounded to 2 decimal places greater than the precision of the original value, up to a maximum of 3 decimal places.

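### The PK Population requires a valid C1D1 predose sample, so a treated patient missing only that sample is excluded from it despite having usable post-dose concentrations

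*Protocol*

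**What the plan says.** Protocol 9.2 (Analysis Populations) sets the PK Population as "All patients who receive study drug and have at least 1 pre- (C1D1) and 1 postdose valid assessment". The predose and post-dose conditions are joint, and the predose one is tied to C1D1. The Pharmacodynamic Population in the same section is looser: "All patients who receive study drug and have at least 1 valid pharmacodynamics/biomarker assessment".

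Protocol 5.2, exclusion criterion 1, is "Previous treatment with camidanlumab tesirine".

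Protocol 7.5.1 names three analytes: "The PK profile of camidanlumab tesirine PBD-conjugated antibody, total antibody, and unconjugated warhead SG3199 will be assessed in serum". Table 4 in that section schedules the one C1D1 sample before the first infusion as "Predose (preferably within 2 h prior to start of infusion"), followed by samples at end of infusion, 4 h, Day 8 and Day 15, and more in later cycles.

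Protocol 9.9 says that "PK parameters will be determined for all PK-evaluable patients" by a non-compartmental analysis. It does not define PK-evaluable. It adds that "Supplemental integrated population PK analyses will be undertaken and reported separately", without naming the population for that work.

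SAP 4.1 lists five populations, none of them for PK. The opening of SAP Section 4 states: "Missing data will not be imputed, except via censoring in survival analyses and as otherwise specified". SAP 8.1.1 closes by ruling out any imputation beyond what it lists, and nothing it lists concerns concentrations.

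**The concern.** A predose sample at first dose normally confirms that there is no drug on board. Here eligibility already makes that the expected result, because nobody may have had the study drug before. The definition still makes the sample a condition of entry. One missed, mishandled or unassayable tube then excludes a patient whose later samples are all usable.

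The contrast within Protocol 9.2 is telling. The pharmacodynamic endpoints are changes in blood biomarkers, for which a baseline is needed and cannot be presumed zero, yet that population needs only one valid assessment. The PK rule is stricter where the baseline is far more predictable.

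At stake is some precision in a secondary endpoint, the concentrations and PK parameters of the three analytes. There is also some ambiguity: valid is not defined, so it is unclear whether an unassayable predose result for one analyte excludes the patient for all three.

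**Working it through.** The plan states no figure on this point, so there is none to reproduce. The check has three parts.

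**1. Does anything else in the plan restore the patient?**

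- Protocol 9.2: both conditions must hold, and no exception is given.
- Protocol 9.9: PK-evaluable has no definition of its own, so the natural reading is membership of the PK Population.
- SAP 4.1: no PK population, so the rule is neither relaxed nor refined.
- SAP Section 4 (opening) and 8.1.1: no rule sets a missing predose concentration to zero.

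Nothing does.

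**2. How much data sits behind one missing sample?** Scheduled PK samples after the first dose, from Table 4:

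| Period | Samples | Count | Running total |
|---|---|---|---|
| Cycle 1 | end of infusion, 4 h, Day 8, Day 15 | 4 | 4 |
| Cycle 2 | predose, end of infusion, 4 h, Day 8, Day 15 | 5 | 9 |
| Cycles 3 to 6 | predose and end of infusion, 4 × 2 | 8 | 17 |
| EOT | one sample | 1 | 18 |

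From Cycle 7 there is one further predose sample per cycle. Seventeen is the count for a patient dosed through Cycle 6; one who stops after Cycle 2 has 9, plus EOT.

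The missing value matters little to what would be computed. Cmax and Tmax do not use it. Cycle 2 has its own predose sample. Cycle 1 AUC needs a concentration at time zero, and exclusion criterion 1 makes zero the expected value.

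**3. How many patients, and at what cost in precision?** The documents give no rate *m* of missing or invalid C1D1 predose samples, so *m* is an assumption. With N = 100 (Protocol 9.1):

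- expected patients lost = N × m
- chance of losing at least one = 1 − (1 − m)^N, taking patients as independent
- relative CI width = 1/√(1 − m), since width scales with 1/√n at a fixed standard deviation

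| Assumed m | Expected lost | Chance of at least one | CI width |
|---|---|---|---|
| 1% | 1 | 63% | +0.5% |
| 2% | 2 | 87% | +1.0% |
| 5% | 5 | 99% | +2.6% |
| 10% | 10 | >99.9% | +5.4% |

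For example, at m = 5%: 100 × 0.05 = 5; 1 − 0.95^100 = 0.994; 1/√0.95 = 1.026. At the upper enrolment of 110 (Protocol 9.4), 2% to 5% gives 2.2 to 5.5 patients.

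**The case against.** **The zero is an inference.** Exclusion criterion 1 covers the study drug only. Exclusion criterion 3 bars patients with known hypersensitivity or positive ADA to a CD25 antibody, so earlier exposure to another CD25 antibody without those features is possible. Total antibody is one of the analytes, soluble CD25 is present in these patients, and neither document describes assay specificity or background. A measured predose value checks all this patient by patient. This stands, and it defeats the stronger reading that the predose condition adds nothing to validity. It supports collecting the sample and reviewing non-zero results; it does not support excluding patients who lack it.

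**Leaving the PK Population is not the same as losing the data.** A reader might infer that the whole profile is lost to the trial, and that the population PK, concentration-QTc, exposure-response and ADA work suffers too. The documents do not support that. Protocol 9.9 reports the population PK and QTc work separately and names no population for either. The exposure-response analysis is exploratory, again with no stated population. Protocol 9.10 uses patients tested for ADA as its denominator. SAP Section 4 also says in general terms that all available data are used. That sentence does not override a specific population definition, but it fits with the concentrations being listed and used elsewhere. What remains is exclusion from the PK Population and, on the natural reading, from the non-compartmental summaries.

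**The effect is small and its size assumed.** This stands. The sample is taken at the dosing visit with a lenient window, which makes a miss less likely. No bias is argued, only a slight loss of precision.

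**The repair takes more than one line.** This also stands: the SAP has no PK population and bars unlisted imputation, so it needs both a definition and an exception.

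**Conclusion.** The point holds in a limited form. As written, Protocol 9.2 excludes a treated patient from the PK Population for want of a single sample whose study-drug concentration is expected to be below quantification. If PK-evaluable means the PK Population, that patient also leaves the non-compartmental summaries in the CSR, with up to 17 scheduled samples after the first dose through Cycle 6.

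At an assumed 2% to 5% missing rate among 100 patients, the loss is 2 to 5 patients and CI widths grow by about 1.0% to 2.6%. This rests on three assumptions: the missing rate, which the documents do not give; the natural reading of PK-evaluable; and a near-zero predose value inferred from exclusion criterion 1.

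The primary ORR and safety analyses use the All-Treated Population and are untouched. Loss in the population PK, QTc, exposure-response or ADA analyses is not shown. This is an improvement worth making, not a threat to the trial's conclusions.

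**What to change.** - In Protocol 9.2, define the PK Population as all treated patients with at least one valid post-dose concentration. Say what makes a concentration valid and whether this is judged per analyte.
- In Protocol 9.9, use the same definition for PK-evaluable.
- Add the population to SAP 4.1, and add an explicit exception to the no-imputation rule: a missing C1D1 predose concentration is taken as zero for Cycle 1 AUC.
- Keep collecting the C1D1 predose sample, and flag measured non-zero values for review.

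The cost is one revised definition, one SAP population and one SAP imputation exception, with no change to sampling or operations. The downside is small: for the few patients without the sample, there is no individual check on assay background.

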9.3 Interim Analysis

No formal interim analysis is planned.

9.4 Final Analysis

For primary and key secondary endpoints analyses, a database snapshot will be taken when all patients who achieve PR or CR have a minimum of 12 months follow-up after initial documented response (may be less for patients undergoing HSCT). All efficacy, safety, and PK endpoints will be analyzed and reported in the clinical study report (CSR).

The exact binomial test will be used in the final analyses for the primary endpoint because of the practical consideration that accrual cannot be limited to exactly 100 patients (\leq 110 patients expected, see Table 7).

Table 7 Number of Responses Needed to Have 95% CI Low Bound of ORR >35%

Total Patients Enrolled	100	102	105	108	110
Number of Responders	45	46	47	49	49
Lower Bound of 95% Exact CI	35.03%	35.22%	35.05%	35.76%	35.07%

Follow-up analyses will be performed when all the patients complete the study per protocol. The results will be reported in a CSR addendum.

9.5 Demographics and Baseline Characteristics

Demographics and Baseline characteristics, such as cancer history and medications history, will be summarized for the All-Treated Population.

9.6 Exposure to Treatments

Exposure to study drug, prior, and concomitant medications will be summarized for the All-Treated analysis set by dose level. Dose interruptions, reductions, and relative dose intensity will also be summarized.

9.7 Efficacy Analyses

Primary efficacy analyses will be based on response as determined by central review. Response reported by Investigators will be used for sensitivity analyses.

9.7.1 Overall Response Rate

The ORR will be defined as the proportion of patients with a best overall response (BOR) of CR or PR. The overall response category will be derived based on response assessment performed on or before the start of subsequent anti-cancer therapy. For the primary ORR analysis in the all-treated population, patients with a CR or PR will be counted as successes and all other patients (including those with missing response information) will be counted as failures.

The percentage of ORR with its 95% confidence interval (CI) will be presented. In contrast to CR, PR, or PD, a BOR of SD can only be made after the patient is on-study for a minimum of 35 days after the first dose of study drug. Any tumor assessment indicating SD before this time period will be considered as a non-evaluable for BOR if no assessment after this time period is available.

9.7.2 **Duration of Response**

The DOR will be defined among responders (CR or PR) as the time from the earliest date of first response until the first date of either disease progression or death due to any cause. The date of disease progression will be defined as the earliest date of disease progression based on central review. For patients who have not progressed or died at the time of the analysis, censoring will be performed using the date of the last valid disease assessment prior to

initiation of a new anticancer therapy (including HSCT). A sensitivity analysis of DOR is planned to be conducted in which the DOR for patients undergoing SCT is not censored at the last evaluable disease assessment prior to SCT. The data will be analyzed by the Kaplan-Meier method. The median DOR and 95% CI will be presented. DOR will be analyzed by response subgroup (CR, PR). Further details will be outlined in the SAP.

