Characterize additional efficacy endpoints of camidanlumab tesirine	 DOR defined as the time from the first documentation of tumor response to disease progression or death CR rate defined as the percentage of treated patients with a best overall response (BOR) of CR Relapse-free survival (RFS) defined as the time from the documentation of CR to disease progression or death Progression-free survival (PFS) defined as the time from first dose of study drug until the first date of either disease progression or death due to any cause Overall survival (OS) defined as the time from first dose of study drug until death due to any cause Fraction of patients receiving hematopoietic stem cell transplant (HSCT).
Characterize the safety profile of camidanlumab tesirine	 Frequency and severity of AEs and SAEs Changes from Baseline of safety laboratory values, vital signs, Eastern Cooperative Oncology Group (ECOG) performance status, and 12-lead electrocardiograms (ECGs)
Characterize the PK profile of camidanlumab tesirine	 Concentrations and PK parameters of camidanlumab tesirine total antibody, PBD-conjugated antibody, and unconjugated warhead SG3199
Evaluate the immunogenicity of camidanlumab tesirine	• Frequency of confirmed positive anti-drug antibody (ADA) responses, their associated ADA titers and, if applicable, neutralizing activity to camidanlumab tesirine after treatment with camidanlumab tesirine

Objectives	Endpoints
Evaluate the impact of camidanlumab tesirine treatment on health-related quality of life (HRQoL)	 Change from Baseline in HRQoL as measured by EuroQoL-5 Dimensions – 5 Levels (EQ-5D-5L) and Functional Assessment of Cancer Therapy – Lymphoma (FACT-Lym)
Exploratory	
Assess the pharmacodynamic effects of camidanlumab tesirine	• Changes in levels of immunologically relevant biomarkers in blood such as but not limited to IL-2, IL-10, and soluble CD25 (sCD25)
Characterize tumor and tumor-associated non-tumor cells (TANT), as well as immunological relevant parameters in tumor tissue	 Measurement of CD25(+) tumor cells and TANT in baseline tumor tissue Measurement of tumor infiltrating lymphocytes (TILs) and other immunologically relevant parameters in baseline tumor tissue

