7.3 Efficacy Assessments

Disease assessments will occur as per SoE (Table 1) until progression.

Screening (Baseline) imaging must be performed within 4 weeks prior to C1D1.

During the treatment period, imaging will be performed 6 weeks and 12 weeks after C1D1, then every 9 weeks until EOT. Week 6 imaging should be performed within 1 week prior to C3D1 and Week 12 imaging should be performed within 1 week prior to C5D1. All other imaging should be performed within ±2 weeks of the scheduled time point. Disease assessments should take place at the timepoints specified even if study drug dosing is delayed.

During the follow-up period, patients who discontinued study drug for reasons other than disease progression or initiation of other anti-cancer therapy will have imaging performed every 12 (± 2) weeks until 1 year from EOT, then every 6 months until disease progression, up to 3 years from EOT; when patients discontinue the study drug because they are planned to undergo a HSCT or to receive CAR-T therapy, imaging will continue the same way. Moreover, HSCT information such as but not limited to type of HSCT, conditioning therapy

should be recorded in the eCRF. Likewise for CAR-T therapy, the type of CAR-T used including conditioning therapy should be recorded in the eCRF.

If a scan has been performed within 6 weeks of EOT, it does not need to be repeated at EOT.

Additional disease assessments may be obtained, if clinically indicated.

Positron emission tomography-computed tomography (PET-CT) of the neck/chest/abdomen/pelvis and other areas of known disease or newly suspected disease, as well as a clinical examination for lymphoma, will be performed. If it is known that the tumor is tracer-avid, the baseline CT as part of the PET-CT does not have to be performed with contrast medium; however, if the tumor is not tracer-avid, diagnostic CT should be used and contrast medium considered, however patients who have a contraindication to CT IV contrast medium should have MRI examinations performed instead. The assessment method determined to identify sites of disease at Baseline (i.e., PET-CT, CT, MRI) should be used for all subsequent assessments.

Patients whose tumor is not PET-avid should have a bone marrow biopsy as part of their baseline staging and disease assessment if clinically appropriate.

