4.9.2 Duration of Response

Duration of response will be defined for patients with CR or PR only as the interval between the date of initial documentation of a response and the date of the first documented evidence of progressive disease based on independent radiographic assessment or death, whichever occurs first. Clinical progression at EOT/EOS without radiographic assessment could be considered as an event in a sensitivity analysis. Patients who have the event after the start of subsequent anticancer therapy/procedure, or are progression-free and alive at the time of

clinical cut-off, or have unknown status, will be censored at the last valid tumor assessment on or before the start of subsequent anticancer therapy/procedure or clinical cut-off time.

Patients with no post-baseline disease assessment will be censored on Day 1.

Duration of response will be estimated and displayed for the all-treated population using Kaplan-Meier methods (SAS® PROC LIFETEST). A Kaplan-Meier plot will be presented.

A sensitivity analysis of DOR will be conducted in which the DOR for patients undergo SCT will not be censored at SCT.

A sensitivity analysis of DOR per investigator assessments will also be conducted.

Subgroup analysis may be provided for disease subtype, disease stage, age group, sex, response to the first line and/or most recent line of prior systematic therapy (relapse: CR+PR vs. refractory: SD+PD vs. other: NE + missing), best response to camidanlumab tesirine (CR/PR), and other relevant variables.

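### DOR is timed from first response but SAP 4.9.2 splits it by best response, so late PR-to-CR conversions tilt the CR-versus-PR comparison towards CR

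*Protocol*

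**What the plan says.** - **Clock.** Protocol 9.7.2 measures DOR among responders "as the time from the earliest date of first response until the first date of either disease progression or death due to any cause". SAP 4.9.2 has the same origin: "the interval between the date of initial documentation of a response and the date of the first documented evidence of progressive disease".
- **Split.** Protocol 9.7.2 states "DOR will be analyzed by response subgroup (CR, PR". It does not say whether first or best response is meant, and leaves detail to the SAP. SAP 4.9.2 supplies it, in a list of optional subgroup variables: "best response to camidanlumab tesirine (CR/PR), and other relevant variables".
- **Who counts as CR.** Protocol Table 2 has "CR rate defined as the percentage of treated patients with a best overall response (BOR) of CR". On that basis a PR that later deepens is a CR.
- **Scans.** Protocol 7.3: "imaging will be performed 6 weeks and 12 weeks after C1D1, then every 9 weeks until EOT". That means Weeks 6, 12, 21, 30 and so on.
- **Safeguards.** For the DOR split, neither document sets a landmark, treats CR as time-dependent, or warns about reading the two curves against each other. RFS (Protocol 9.7.4, SAP 4.9.5) starts at first CR and covers CR patients only. The DOR method is Kaplan-Meier, with no CR-versus-PR test.

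**The concern.** The time origin and the grouping variable are fixed at different moments. A patient with PR at Week 6 who becomes CR at Week 12 has 6 weeks (1.4 months) of DOR during which progression was impossible by construction. With conversion at Week 21 it is 15 weeks (3.4 months). A patient with PR at Week 6 who progresses before converting stays in the PR group. Membership among initial PRs therefore depends on the outcome being measured, which is guarantee-time (immortal-time) bias.

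The stake is interpretive. Two Kaplan-Meier curves with medians side by side invite the reading that deeper response lasts longer, and part or all of the visible separation could come from the classification rule. RFS gives CR durability from a sound origin but has no PR counterpart, so it does not repair the comparison.

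**Working it through.** **The plan's own figure.** There is none for DOR by response group. The size below therefore rests on assumptions, shown as a range.

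**Inputs from the documents.** Scans at Weeks 6, 12, 21 and 30 (Protocol 7.3). Phase 1 at 45 µg/kg had 18 CR and 14 PR (Protocol 1.3), so CRs were 18/32 = 56% of responders. This is used only to keep the scenarios plausible.

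**Assumed.** All first responses occur at Week 6. Time to progression is exponential with the same median M (6, 9 or 12 months) for every responder, so the true CR-PR difference is zero. A share p is CR at Week 6. A share c of the remaining progression-free PRs converts at each of Weeks 12, 21 and 30, unrelated to prognosis.

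**Formulas.** S(t) = 2^(−t/M). The conversion scans fall u = 1.38, 3.45 and 5.52 months after first response.
- P(CR) = p + Σ (1−p)(1−c)^(k−1) c S(u_k)
- P(CR)·S_CR(t) = p S(t) + Σ (1−p)(1−c)^(k−1) c S(max(t, u_k))
- P(PR)·S_PR(t) = S(t) − P(CR)·S_CR(t)

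The term max(t, u_k) is the guaranteed time.

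**Worked case: M = 9, p = 0.30, c = 0.20.**
- S(u) = 0.899, 0.767, 0.654.
- Late CRs: 0.7×0.2×0.899 + 0.7×0.8×0.2×0.767 + 0.7×0.64×0.2×0.654 = 0.126 + 0.086 + 0.059 = 0.270.
- P(CR) = 0.570; late share of CRs = 0.270/0.570 = 47%.
- CR median: S(t) = 0.5 × 0.570/(0.30 + 0.7×0.488) = 0.444, so t = 10.5 months.
- PR median: S(t) = 0.5 × 0.430/(0.7×0.512) = 0.600, so t = 6.6 months.
- Spurious gap: 3.9 months.

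**Range (median DOR in months, CR / PR; true difference zero).**

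| CR at first scan | Conversion per later scan | Late share of CRs | M = 6 | M = 9 | M = 12 | Gap |
|---|---|---|---|---|---|---|
| 56% | 0% | 0% | 6.0 / 6.0 | 9.0 / 9.0 | 12.0 / 12.0 | 0 |
| 50% | 5% | about 10% | 6.3 / 5.6 | 9.4 / 8.5 | 12.4 / 11.5 | 0.8 to 0.9 |
| 45% | 10% | about 20% | 6.7 / 5.1 | 9.7 / 8.0 | 12.7 / 10.9 | 1.6 to 1.8 |
| 30% | 20% | 45 to 49% | 7.5 / 4.2 | 10.5 / 6.6 | 13.6 / 9.5 | 3.3 to 4.1 |

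All four rows end with 54 to 59% of responders in CR, in line with Phase 1, so the final CR share does not tell us which row applies. At the extreme where every CR is late (50% conversion at Weeks 12 and 21), simulation gives 8.0 / 2.6 for M = 6 and 14.1 / 7.0 for M = 12.

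**As hazard ratios (simulation, conversion at Weeks 12 and 21).** The best-response split gives a CR:PR ratio of 1.00 with no late conversion and 0.76 (M = 6) or 0.85 (M = 12) with about half of CRs late. If someone added a nominal 5% log-rank test with 55 responders (100 × the design ORR of 55%) and 12 to 24 months of follow-up, it would reject in 5 to 6% of trials with no late conversion and in 14 to 23% with about half late.

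**Does the remedy work?** In the p = 0.30, c = 0.20 setting, a Week 12 landmark gave equal medians in both groups (6.0/6.0, 9.0/9.0, 12.0/12.0). A landmark at the last conversion scan, or CR as a time-dependent state, gave ratios of 0.99 to 1.01 in every scenario run.

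**Limit.** These medians use the actual progression time. With progression seen only at scans, medians move in steps: for M = 6 with 17% of CRs late, both groups show 7.6 months. A small bias may then be invisible in the medians.

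**The case against.** Several objections have force.

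- **Only converters carry guaranteed time.** A reader might infer that the whole CR group is protected, or that every early progressor ends up as PR. Neither follows. A patient already in CR at the first scan has no guaranteed time and, on early progression, still counts as CR.
- **The size is unknown.** A reader might infer a gap of several months. That requires nearly half of CRs to be late, and nothing in the documents establishes it. The range starts at zero.
- **The split is descriptive.** A reader might infer that the trial will conclude that CR lasts longer than PR. Neither document plans such a test or claim, and the SAP makes the subgroup optional although the protocol commits to it. As a plain description of patients whose best response was CR, the figure is what it says. It misleads when set against the PR figure as evidence about depth of response.
- **RFS already covers durability of CR** from a proper origin. This stands, but it leaves the comparison with PR unaddressed.
- **The protocol sentence does not say best response.** True. If response at first documentation were meant, this bias would disappear. But the SAP says otherwise, so its text needs changing either way.
- **A landmark is no longer DOR and drops patients.** Also true. That is why it belongs beside the best-response display and not in its place.

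**Conclusion.** The point holds in limited form. As written, SAP 4.9.2 yields a CR-versus-PR display of DOR that favours CR whenever some CRs are late conversions. The direction is certain in that case and the size is not. With equal true durability (median 6 to 12 months), the spurious gap in medians is 0 with no late conversion, about 1 month with roughly 10% of CRs late, about 3 to 4 months with nearly half late, and 5 to 7 months if all are late. This rests on exponential durability, first response at Week 6 and conversion unrelated to prognosis.

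The documents do not support extending this to the trial's main results. The primary ORR does not use the split, overall DOR pools all responders, and RFS starts at first CR. The defect is confined to one descriptive comparison, but it is cheap to correct and better settled in advance.

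**What to change.** In SAP 4.9.2:

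1. Add a prespecified landmark analysis. Classify responders by CR or PR status at the Week 12 scan, include those still progression-free and uncensored, and measure remaining time to progression or death from that date. Treating CR as a time-dependent state is an acceptable alternative.
2. If DOR by best response is also shown, label it descriptive and not for comparing CR with PR, and refer to RFS for durability of CR.
3. State that this is how the protocol's CR/PR commitment is met, and settle it before the database snapshot. A landmark chosen after seeing the data carries less weight.

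Cost: one SAP paragraph and one extra table, with no change to conduct or data collection. Responders who progress before Week 12, are censored before it (including for transplant or new therapy), or first respond after it are left out of the landmark display only. With about 55 responders expected at the design ORR, those groups will be small.
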